Systemic inflammatory response syndrome (SIRS) and pyrexia are frequent conditions after brain injuries making conventional detection of sepsis extremely inaccurate^{1,2}. Early detection of sepsis helps in reducing the secondary injury to brain and the same time accuracy in detection of sepsis is needed to avoid indiscriminate antimicrobial usage and further antimicrobial resistance. Current commonly used biological markers of sepsis like white cell count (WBC) and CRP (C-Reactive Protein) is unspecific for sepsis in this population as they are usually elevated due to the surgery or trauma. Other biological markers such as procalcitonin (PCT), tumour necrosis factor (TNF) and Interleukin-6 have been evaluated but the costs can be prohibitive, delayed due to the processing time and non-specific². Pelinka *et al* has also showed that traditional sepsis markers like CRP and PCT are inaccurate in head injuries^{3,4}. Microbiological culture of bacteria is currently the gold standard for sepsis but processing time takes at least 24 hours and is not specific and is frequently at risk of contamination if not sampled correctly. The indiscriminate use of broad-spectrum antibiotics promotes the selection of antibiotic resistance and has further complications. At the same time, patients presenting with a Sequential Organ Failure Assessment (SOFA) score of 2 or more (which is the new definition of sepsis) have an overall mortality risk of 10% with presumed infection which is greater than overall mortality of 8.1% for ST- segment elevation myocardial infarction⁵. So, clinicians have daily difficulties in deciding if a patient is septic when faced with critically ill patients especially with brain injuries and SIRS.

Background

Activated Partial Thromboplastin Time (APTT) clot waveform analysis (CWA) and WBC activation analysis by flow cytometry-based method are new and very low cost biological tests proposed for the diagnosis of sepsis in the general ICU population. Recent advances in coagulation analysers have enabled the ability to obtain optical profiles of the clotting process for routine tests such as Prothrombin Time and APTT within 1 hour of the sample reaching the laboratory. The analysis using real time optical transmittance to provide more information from the clotting assay than just an endpoint clotting time. The profiles plot change in light transmittance against time, producing a 'wave-like' plot. Abnormal CWA have been seen in many conditions such as trauma and Disseminated intravascular coagulation (DIC) and especially in sepsis. Studies have shown that they predict for severe sepsis, septic shock and DIC^{6,7}. Pilot studies in the general ICU have shown promise in the detection of severe sepsis⁸. Toh *et al* also found that this biphasic waveform was due to the rapid precipitation of CRP, and very-low-density lipoprotein (VLDL) in the presence of calcium ions. CRP belongs to a family of proteins known as pentraxins, and its level rapidly increases under conditions of infection or tissue damage⁹. Presence of abnormal waveforms has been confirmed in severe sepsis in studies performed in the general ICU⁹ and in personal observations in University Hospital Aintree. It was identified that biphasic waveform was more accurate than PCT and CRP for differentiating patients with severe sepsis and septic shock, with 90% sensitivity and 92% negative predictive value^{6,7}. These biphasic waveform values were significantly more abnormal during day 1–3 in septic nonsurvivors than in survivors and nonseptic nonsurvivors and exhibited the best specificity (91%) and negative predictive value (98%) for the prognosis of sepsis-related mortality on day 3⁶. There are no studies have examined the diagnostic value of these novel sepsis measures in the neurosurgical population of subarachnoid hemorrhage, traumatic brain injury and other intracranial hemorrhages.

Routine analysis of WBC using flow cytometry-based method has been shown to be low cost, rapid and can be incorporated as part of the routine full blood count (FBC) analysis. During stress or infection, less mature neutrophil forms enter circulation, including an increased number of bands. This is referred to as a left shift, which is defined as an elevated immature/total granulocyte ratio or an

elevated neutrophil band count. Neutrophil and monocyte activation has been shown to correlate well in laboratory studies and in pilot clinical studies on septic ICU patients¹⁰. Linssen et al showed that using the Sysmex XE-2100 analyser allowed the real time study of monocyte and neutrophil activation by using the routine fluorescence-flow cytometer of the analyser. The information about cell shape, cell membrane content and cell granularity, thus giving an idea as to WBC activation status. The 'Neutrophil X' (NEUT-X) parameter measures neutrophil granularity. The more the cells degranulate (in response to sepsis), the lower the parameter value becomes. The 'Neutrophil Y' (NEUT-Y) parameter measures the production and release of proteins (reactive oxygen intermediates and cytokines) from neutrophils by a change in nucleic acid content. The immature granulocyte parameter (IG) parameter and neutrophil reactive index (NEUT-RI) also correlates with sepsis. Wiemann et al (2015) has used a composite score, Intensive care Infection Score (ICIS) in medical-surgical ICU patients to differentiate between with infection and without infection with high sensitivity and specificity¹¹. The ICIS comprised of five blood-cell derived parameters that characterize the early innate immune response: (I) mean fluorescence intensity of mature (segmented) neutrophils; (sNGI) (II) difference in haemoglobin concentration between newly formed and mature red blood cells;(dChC) or delta-Hemoglobin (III) total segmented neutrophil count;(sN#) (IV) antibody secreting lymphocyte count;(ASL) (V) immature granulocyte count(alG). In the study, an ICIS score of more than 3 was considered as positive score for sepsis using a modified fully automated routine fluorescence hematology analyser (XN-10; Sysmex, Kobe, Japan). This can be measured during the WBC measurement and does not require any additional blood sampling.

2. Study Aims and Significance

Primary Aim

To validate the use of APTT CWA and ICIS, as early sepsis markers for neurosurgical ICU patients suffering subarachnoid haemorrhage, traumatic brain injury and other intracranial haemorrhages.

Secondary Aim

To examine the evolution of CWA, immuno-parameters (KL-6, SP-A, MIG, presepsin) and various WBC activation markers over the time in relation to diagnosis of sepsis, development of positive blood cultures and mortality or recovery. Blood parameter measurements using a 3-part and 5-part differential analyser will be performed.

Potential Risks

This will purely be an observational study of changes in laboratory parameters and the research participants do not deviate from the current standard of care. However minimal risks are anticipated for this study as all additional blood samples collected are from arterial lines inserted as part of routine care for patients in the SICU.

Potential Benefits

There is no assurance that the research participants will benefit from participation in this study. However, their participation in this study may add to the medical knowledge by exploring novel early predictors and validation of laboratory parameters in the management of sepsis. This will greatly complement current clinical monitoring of patients in the SICU without subjecting the patients to additional invasive tests.

Study Significance

The research study is to explore novel early predictors and validation of laboratory parameters in the management of sepsis. This will greatly complement current clinical monitoring of patients in the SICU without subjecting the patients to additional invasive tests.

3. Study Design

This is a prospective observational study. 150 subjects with the admission diagnosis of neurological haemorrhage (e.g. subarachnoid haemorrhage, intracerebral haemorrhage etc), admitted to SICU of National University Hospital, Singapore, who are expected to stay for more than 48 hours, will be recruited and enrolled. The proposed workflow for this study is highlighted in Figure 1. No adverse events are expected as a result of this study as patients do not deviate from the current standard of care. Frequency of blood sampling will be stipulated at day 1/2/3/4/5 to draw clinical relevance. An additional 0.5 tablespoonful (7.7ml) of blood will be taken daily from each subject as well as residual blood from routine laboratory test blood samples. In total, an additional volume of 2.5 tablespoonful (38.5ml) of blood will be collected from each subject over a period of 5 days. Residual blood refers to any leftover blood samples collected for routine laboratory tests which will be shared and used to carry out additional blood tests as shown in Table 1. All ICU patients will have arterial lines inserted as part of routine care, so there will not be pain from the blood sampling. In the current study, measurements will be made on the routine laboratory haematology, coagulation and immunoassay analyzers. Research blood parameters that are not usually reported as indicated in the background section will be used for the correlation and association analysis to sepsis. Over a period of 2 years, these blood samples will be collected from 150 patients, stored in -80 degrees' freezer and then used for batch standard laboratory tests. The remaining blood samples will be stored in NUH in -80 degrees' freezer over a period of 5 years for future biomedical research use.

In addition, the study team will also be collecting clinical and demographic data of recruited subjects from medical records for purposes of this study.

[figure not shown]

Figure 1. Proposed flow chart for research project

#The diagnosis of sepsis is obtained from the treating physician or the commencement of antibiotics and confirmed by microbiological cultures (routinely performed during this period as the standard of care to detect sepsis). The treating physician will not be involved in data analysis of CWA, immunoparameters and WBC infection score. Results will be stratified based on patients who have no SIRS, SIRS but no microbiological evidence of sepsis (via blood, sputum, urine cultures etc), sepsis (SIRS + microbiological evidence) and retrospectively analysed. The patient will be treated according to the treating physician's routine standard of care practices in the best interest of the patient. No potential adverse events are expected as this will purely be an observational study of changes in laboratory parameters.

Source of sepsis secondary to ventilator associated pneumonia is defined according to the new CDC guideline for definition which includes

- Definition of ventilator associated event plus, on or after calendar day 3 of mechanical ventilation and within 2 calendar days before or after the onset of worsening oxygenation, following criteria to be met
- Criteria one: Positive culture of one of the specimens meeting quantitative or semi quantitative thresholds (Endotracheal aspirate $>10^5$ CFU/ml; Bronchoalveolar lavage $>10^4$ CFU/ml; Lung tissue $>10^4$ CFU/ml and protected specimen brush $>10^3$ CFU/ml without need for purulent secretions
- Criteria two: Purulent respiratory secretions plus organism identified from one of the above specimens without sufficient growth to meet criterion 1
- Definition of bacteraemia is by presence of positive blood cultures
- Catheter associated Urinary tract infection is defined as presence of positive urinary microscopic examination of more than 5 WBC from the freshly placed urinary catheter long with positive urinary cultures

Table 1. Blood volume required for investigation

Blood volume collection and testing:					
#Standard of Care Blood Investigations	DAY 1	DAY 2	DAY 3	DAY4	DAY 5
FBC (EDTA/Lavendar top)	3ml*	3ml*	3ml*	3ml*	3ml*
CRP (SSTII/Red Top)	5ml**	-	5ml**	-	5ml**
Blood cultures (routine ICU care for fever)	10ml	-	10ml	-	10ml
CREATININE (SSTII/Red Top)	5ml**	5ml**	5ml**	5ml**	5ml**
Additional blood investigations:					
FBC (3-Part Diff) (EDTA /Lavendar Top)	3ml*	3ml*	3ml*	3ml*	3ml*
PTINR/APTT (Citrate/Blue Top)	2.7ml	2.7ml	2.7ml	2.7ml	2.7ml
PROCALCITONIN (SSTII/Red Top)	5ml [§]	-	5ml [§]	-	5ml [§]
Serological/Inflammatory Markers (KL-6, SPA, MIG, Presepsis)(SSTII/Red Top)	5ml [§]				

Actual blood investigation may vary depends on patient's clinical conditions
Volume marked with *, **, [§] indicate sharing of blood tube for testing.

Note:

- 7.7ml of additional blood (highlighted in yellow) is taken for this study daily over 5 days for these additional blood tests: APTT, Procalcitonin and Serological/Inflammatory markers (KL-6, SPA, MIG, Presepsis). All other bloods are routinely taken for routine investigations during their SICU stay.
- Out of the 7.7ml of additional blood, 5ml of blood drawn will be shared and used for these blood tests: Procalcitonin and Serological/Inflammatory markers (KL-6, SPA, MIG, Presepsis) as marked with this symbol §.

4. Patient Recruitment

List the number of subjects to be enrolled

A total target number of 150 subjects with the admission diagnosis of neurological haemorrhage (e.g. subarachnoid haemorrhage, intracerebral haemorrhage etc), admitted to SICU of National University Hospital, Singapore, who are expected to stay for more than 48 hours, will be recruited and enrolled.

Criteria for recruitment

The SICU anaesthetist on duty would make first contact with potential participants of the research study. After obtaining consent, the SICU anaesthetic team will then make the necessary referral to the study team members who will then screen for their eligibility based on the subject eligibility checklist. These potential participants will be recruited by face-to-face contact via their legally acceptable representative when they are in SICU.

Inclusion criteria for subjects:

- Adults 21 years and above
- Clinical/radiological suspicion or confirmation of neurological haemorrhage

Exclusion criteria for subjects:

- Age below 21 years
- Prisoners
- Known pregnancy
- Do-not-attempt resuscitation status
- Requirement for immediate surgery
- Active chemotherapy/neutropenia (Neutrophil count $<1.0 \times 10^9/L$)
- Immuno-compromised
- Haematological malignancy
- Treating physician deems aggressive care unsuitable
- Unable to provide informed consent or comply with study requirements

Patient withdrawal

Patients will be allowed to withdraw anytime during the study without comprising their care.

Subject Replacement

Subjects who drop out will not be replaced to reach the minimum target number.

5. Data Collection

Data will be collected for all tests performed (raw data format and instrument files) and the clinical data includes

- Past medical history and demographic data
- Presence of SIRS; timing of sepsis and septic shock
- APACHE II, SOFA and other disease severity scoring systems
- Routine blood tests such as CRP and/or PCT
- Timing of Blood cultures and therapies (Inotropes and antibiotics etc.)
- Longitudinal test results to include PT/aPTT CWA, FBC, WBC infection scores including ICIS and related parameters (marked as ICU day 1 to day 5), immuno-parameters (KL-6, SP-A, MIG, Presepsin)
- Complications
- Length of ICU stay and mortality

6. Study Outcomes

The primary analysis of the study is to examine a number of laboratory test parameters and its association to sepsis as the clinical outcome. The associations between the presence or absence of the biphasic wave form in CWA, WBC activation parameters and clinical relevance of immuno-parameters at baseline and subsequent diagnosis of sepsis.

Secondary analysis will examine the potential predictive value of evolution of CWA and WBC parameters over time in relation to the diagnosis of sepsis, development of positive blood cultures and mortality.

7. Data Analysis

Data Quality Assurance

The study team will ensure that the data obtained from this research is accurate, complete and reliable.

Data entry and Storage

The data will be entered into excel sheet, and then be stored and handled.

8. Sample size and Statistical methods

Determination of sample size

This is a pilot study to determine the resources needed for a full scale study, thus 150 has been selected as the recruitment target.

Statistical and Analytical Plans

In order to assess the ability of baseline CWA, immuno-parameters and ICIS to discriminate between septic and non-septic patients, a receiver operator characteristic (ROC) curve will be constructed for each measure against presence of sepsis as determined by the treating physician (SIRS), and by microbiological culture of bacteria (severe sepsis). As a result, the sample size is based on that needed to evaluate the area under the ROC curve. We assume that an AUC of 0.7 (while better than chance) would be insufficiently discriminating, but as one aim of the study is to estimate the AUC, a value of 0.85 has been set as the value expected. If this is the true value, then the sample size to rule out a value of 0.7 or less, with 80% power and one-sided significance of 5% is 98 patients, assuming the proportion of patients with sepsis is at least 25%.

Simple descriptive statistics (proportions and accompanying confidence intervals) will be used to assess complication rates and other frequency data. Continuous measures will be assessed using mean and standard deviation (or median and interquartile range if the distribution is non-symmetrical). A number of further exploratory analyses may then be undertaken. Simple line plots of CWA and WBC activation parameters for each patient over time and summary measures or relevant repeated measures regression techniques may be considered. If feasible this may include the analysis of the relationship between sepsis confirmation and measures of CWA, immuno-parameters and ICIS over time. Time to event analyses may also be undertaken using standard techniques (e.g. Kaplan-Meier plots, Cox proportional hazards models) to compare the survival prospects and/or time to sepsis for patients with and without SIRS or severe sepsis at baseline.

9. Ethical Considerations

Informed consent

Informed consent will be obtained prior to performing any study-related procedures. The informed consent process will be taken at SICU via the potential participants' legally acceptable representative (LAR). The LAR would be given sufficient time to decide whether to let them participate in the research study. The consent will be conducted in a private room in SICU together with participants' LAR. The wishes of the participant's LAR must also be respected if they chose not to allow the participant to take part in the research study.

IRB review

Each participating institution must provide for the review and approval of this protocol and the associated informed consent documents by the IRB/ NHG DSRB/ SGH CIRB.

Confidentiality of Data and Patient Records

For hardcopy data, they will be stored in designated locked cabinet(s) or room(s) that are accessible to authorized study personnel only.

For electronic data, they will be stored on in a secured computer that is password protected. The databases will not contain subject identifiers and the data linking subject identifiers and the subject identification codes will be stored separately.

10. Retention of study documents

Records for all participants, including CRFs, all source documentation (containing evidence to study eligibility, history and physical findings, laboratory data, results of consultations, etc.) as well as IRB records and other regulatory documentation should be retained by the PI in a secure storage facility for 6 years or minimum duration of retention period as specified by the institutional policy. The records should be accessible for inspection and copying by authorized authorities.

References:

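### The section 8 ROC sets septic against all non-septic patients, so on the culture-labelled curve the AUC does not isolate sepsis from SIRS without infection, which is the problem the Background poses

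*Protocol*

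**What the plan says.** The Background explains that SIRS is common after brain injury and that "clinicians have daily difficulties in deciding if a patient is septic when faced with critically ill patients especially with brain injuries and SIRS".

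Section 3 (note on the diagnosis of sepsis, below Figure 1) sets up groups that match this problem: "Results will be stratified based on patients who have no SIRS, SIRS but no microbiological evidence of sepsis", and sepsis, defined there as SIRS plus microbiological evidence. Below, *sterile SIRS* means SIRS without microbiological evidence.

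Section 8 (Statistical and Analytical Plans) uses a two-way split. Baseline CWA, immuno-parameters and ICIS are to "discriminate between septic and non-septic patients, a receiver operator characteristic (ROC) curve will be constructed for each measure", and the curves are drawn "against presence of sepsis as determined by the treating physician (SIRS), and by microbiological culture of bacteria (severe sepsis"). The performance values attach to this split: "We assume that an AUC of 0.7 (while better than chance) would be insufficiently discriminating"; "a value of 0.85 has been set as the value expected"; and "the sample size to rule out a value of 0.7 or less, with 80% power and one-sided significance of 5% is 98 patients". The calculation takes a quarter or more of the patients to be septic. Section 8 neither mentions the three groups nor restricts the non-septic patients to those with SIRS. Section 4 does not require SIRS for entry, so patients without it can be enrolled.

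**The concern.** An AUC depends on who serves as the control. Patients with no SIRS are likely to be easier to tell from septic patients than patients with sterile SIRS are, at least for a marker that follows inflammation in general. The Background itself says that the biphasic waveform arises from CRP precipitation, that CRP rises with infection or tissue damage, and that abnormal waveforms occur in trauma.

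If both kinds of control are pooled, the AUC mixes the contrast clinicians find hard with an easier one, in proportions set by who happens to be recruited. A marker that does poorly against sterile SIRS could then show an AUC well above 0.70, and a reader could take that as evidence that it separates sepsis from SIRS.

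**Working it through.** **Inputs from section 8:** null AUC 0.70, expected AUC 0.85, one-sided 5%, 80% power, 98 patients, 25% septic. Target enrolment is 150 (sections 3, 4 and 8), so 0.25 × 150 = 37.5, taken as 38 cases and 112 controls.

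**Assumptions (no figures in the protocol):** the share *p* of controls without SIRS (sterile-SIRS share *s* = 1 − *p*), and the AUC against each kind of control. The case label is taken to be section 3's sepsis group.

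**Step 1: the plan's own figure.** Hanley-McNeil variance with *m* cases and *n* controls:

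Var(A) = [A(1 − A) + (m − 1)(Q₁ − A²) + (n − 1)(Q₂ − A²)] / (mn), with Q₁ = A/(2 − A) and Q₂ = 2A²/(1 + A).

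The requirement is 0.15 ≥ 1.645 × SE(0.70) + 0.842 × SE(0.85). At N = 98 (24.5 cases, 73.5 controls) the SEs are 0.0650 and 0.0514. The right side is about 0.150 and power is 79.8%. The smallest N that meets the requirement is 99. The stated 98 therefore reproduces, and the sample-size arithmetic is not at issue.

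**Step 2: AUC against a mixed control group.** This is exactly a weighted mean:

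AUC(pooled) = p × AUC(vs no SIRS) + (1 − p) × AUC(vs sterile SIRS).

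**Step 3: a weak marker.** Take 0.70 against sterile SIRS and 0.95 against no SIRS. With 38 cases and 112 controls, SE(0.70) = 0.0522, so 0.70 is ruled out when the estimate exceeds 0.70 + 1.645 × 0.0522 = 0.786. The probability of that is Φ[(A − 0.786)/SE(A)], treating the Hanley-McNeil SE as adequate for mixed controls.

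| p (controls without SIRS) | Pooled AUC | SE | Probability of ruling out 0.70 |
|---|---|---|---|
| 0.2 | 0.75 | 0.0497 | about 23% |
| 0.3 | 0.775 | 0.0480 | 41% |
| 0.4 | 0.80 | 0.0461 | 62% |
| 0.5 | 0.825 | 0.0439 | 81% |
| 0.6 | 0.85 | 0.0413 | 94% |

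On the restricted contrast, where this marker's AUC is 0.70, the probability would be the nominal 5%.

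**Step 4: a marker that detects only SIRS.** It has AUC 0.50 against sterile SIRS. If it detects SIRS perfectly, the pooled AUC is 1 − s/2. It reaches 0.85 only if s ≤ 0.30 and exceeds 0.70 only if s < 0.60. If its AUC against no SIRS is 0.90, the pooled value is 0.86, 0.82, 0.78, 0.74 and 0.70 at s = 0.1 to 0.5.

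**Step 5: the physician-labelled curve.** Section 8 glosses this label as SIRS. Read literally, sterile-SIRS patients may be cases there, which conflicts with section 3, where they form a separate non-sepsis group. The pooled-control description does not fit this curve. It has a labelling problem instead, and it does not isolate sepsis from sterile SIRS either.

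**The case against.** **Section 3 already stratifies, and a SAP could supply the detail.** Nothing excludes the ROC results from that stratification. However, section 3 links the groups to no ROC, AUC or benchmark, and section 8 states a specific contrast and sizes the study on it. This is two sections not joined up rather than a detail left open. A reader should not infer that the protocol overlooks sterile SIRS altogether.

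**Timing.** This stands. Sections 6 and 8 use baseline markers, with section 6 relating them to a later diagnosis. That every septic patient has SIRS describes status at diagnosis, and a future case may have no SIRS when the sample is drawn. The assumed 0.95 could therefore be too high. The direction remains whenever the marker separates septic patients better from no-SIRS than from sterile-SIRS controls.

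**A marker that only detects SIRS could hit the target.** A reader might infer this as a general statement. The documents do not support it: 0.85 needs sterile SIRS to be at most 30% of controls even with perfect SIRS detection, and the Background calls SIRS frequent. The more relevant case is the weak marker in step 3.

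**The all-comer ROC is legitimate.** This also stands. The primary aim in section 2 covers neurosurgical ICU patients with haemorrhage generally, so septic versus all non-septic is a reasonable question. The documents do not support the inference that it must be replaced as primary.

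**It is a pilot with no decision rule.** Section 8 calls the study a pilot, and 0.70 appears only in the sample-size rationale, so no marker would be formally declared valid. Still, the primary aim is to validate CWA and ICIS, and 0.70 is the protocol's own threshold for insufficient discrimination.

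**Conclusion.** The concern holds in a limited form. On the culture-labelled curve, section 8 pools no-SIRS and sterile-SIRS patients as controls, so the planned AUC does not answer the Background's question of recognising sepsis among patients with SIRS.

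The size of the effect is conditional. It rests on assumed AUCs of 0.70 and 0.95 and on an unknown SIRS share. Under those values the pooled AUC exceeds the restricted one by 0.05 to 0.15 for p = 0.2 to 0.6, and exceeds it less if baseline SIRS status predicts later status poorly. The all-comer ROC is not wrong in itself. It cannot alone support a claim of telling sepsis from SIRS.

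**What to change.** In section 8:

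- Add, for CWA and ICIS, a named and prespecified ROC of sepsis (SIRS plus microbiological evidence) versus SIRS without microbiological evidence.
- State when SIRS status is taken relative to the baseline sample. If it means SIRS at any time, controls are selected on later status that is unknown at sampling.
- Report this AUC beside the all-comer AUC, and let any claim of telling sepsis from SIRS rest on it, judged against 0.70.
- Reconcile section 8's two case labels (glossed as SIRS and as severe sepsis) with section 3's groups.

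**Cost.** Mostly wording. Section 5 already collects the presence of SIRS and the timing of sepsis and blood cultures. It lists no timing for SIRS itself, so a date may have to be recorded.

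The statistical cost is fewer controls and probably a lower AUC. If 60% of the 112 controls have sterile SIRS (67 patients), the SE at AUC 0.85 rises only from 0.0413 to 0.0425. Power against 0.70 is about 92% at a true AUC of 0.85, but 58% at 0.80 and 22% at 0.75. At 0.85, power runs from about 79% to 93% as the sterile-SIRS share goes from 20% to 80% of controls. The restricted AUC should therefore be reported with its confidence interval.
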